### 8.6.3 Evaluate Treatment Effects on Suicidal Thoughts (via M.I.N.I.-Plus Suicidality), Psychological Distress (via the K6), Anxiety Disorders (via GAD-7), Depression (via PHQ-9), Physical and Mental Composite Measures (via SF-12), and Pain (via Short Pain Scale) Across Time

Treatment effect in the improvement or reduction of relevant health and psychological status information such as suicidal thoughts (M.I.N.I.-Plus Suicidality), psychological distress (K6), anxiety disorders (GAD-7), depression (PHQ-9), physical and mental composite measures (SF-12), and pain (short pain scale) will be analyzed using similar modeling techniques as mentioned in section 8.6.2. Modeling techniques with either linear mixed models or generalized mixed models will account for the structure of the outcome measure (continuous, binary, ordinal, nominal). Each model will incorporate treatment, baseline measure, site, time (as categorical variable) and two-way interactions between treatment and time. Other potential covariates or effect modification variables may be included in the model based on a univariate analysis of baseline measures with the specific outcome measure of interest.

Another secondary analysis of interest is to determine the effectiveness of the SGB among the participants for whom the stellate ganglion was anesthetized effectively. The population that will be utilized for this analysis will be defined as the “Horner’s responder population.” This population will be defined as those participants who showed a maximum density of Horner’s syndrome, reflected by scleral injection, meiosis, and ptosis, following the procedure. For analytic purposes, this will include all participants with a Post-Horner’s total score of 12. The analytic approach will mirror that for the primary analysis but will utilize only Horner’s responders from the active treatment arm, with propensity scores based on baseline demographic and clinical characteristics used to define a comparator control population.

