surgical and procedural site verification of patients undergoing operative or other invasive procedures”. In accordance with this regulation, the participant’s identity, the procedure to be performed, and the specific site of the procedure will be verified. A separate paper CRF will be created for the procedure; this information will not be shared with anyone outside the treatment suite (RC, participant, other members of the RTI Project Team, etc.). It is critical that only the physician administering the treatment (and his immediate team) be aware of the participant’s assignment to active or sham intervention. Following the intervention, the treating physician should have no further contact with the participant except as required for participant safety.

Immediately following each SGB procedure, the subject will be observed in the procedure suite prior to transport to the recovery area for assessment of potential complications that could require immediate intervention, according to local clinic policy. The participant then will be taken to the post-procedure recovery area, where monitoring of vital signs will continue under the supervision of the recovery nurse for 20 minutes or longer, again per local clinic policy and participant condition.

The RC will assess the participant at 30 minutes post-procedure for his/her Horner’s syndrome, recording the time post-SGB and using the following metrics (0 for absent, 1 for slight, 2 for obvious) when the participant is sitting up straight and not facing a bright light:

- ptosis
- scleral injection
- miosis

Assuming the absence of complications requiring further evaluation or treatment, the participant will be given discharge instructions, and will be required to verbally indicate understanding of signs and symptoms that would require emergency care (e.g., shortness of breath or difficulty breathing, increasing neck pain). In addition, the clinic nurse will remind the participant that soreness at the injection site, a full sensation of the throat, and Horner’s symptomology may occur for 6-18 hours (the duration of effect of the local anesthetic); if the recurrent laryngeal nerve has been blocked, there may also be hoarseness and difficulty swallowing. The participant then will be allowed to leave the clinic per local site policy.

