Similarly, improvement in physical and mental composite measures (SF-12) due to treatment effect will be analyzed using linear mixed models at each time point, or comparing the scores at different time points. As before, the effects will be adjusted by corresponding baseline measure, site, and concomitant variables and comorbidities relevant to these measures.

Another secondary analysis of interest is to determine the efficacy of the SGB among the participants for whom the stellate ganglion was anesthetized effectively. The population that will be utilized for this analysis will be defined as the “Horner’s responder population.” The

analytic approach will mirror that for the primary analysis but will utilize only Horner's responders from the active treatment arm, with propensity scores as described in the SAP to select the appropriate sub-population among the control arm participants.

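### In the ITT version of the Horner's responder analysis, active participants must have had both injections to qualify, but sham comparators need not have.

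*SAP*

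**What the plan says.** Protocol 8.2 plans a secondary analysis of efficacy in participants whose ganglion was effectively anaesthetised. It takes Horner's responders from the active arm only and leaves the control side to the SAP: "with propensity scores as described in the SAP to select the appropriate sub-population among the control arm participants".

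SAP 8.6.3 describes the responders as showing the maximum density of the syndrome, "reflected by scleral injection, meiosis, and ptosis, following the procedure", and sets the cut-off: "For analytic purposes, this will include all participants with a Post-Horner’s total score of 12". It then says that the approach follows the primary analysis, uses active-arm responders only, and forms the control side "with propensity scores based on baseline demographic and clinical characteristics used to define a comparator control population".

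Protocol 6.3 gives the scoring. "The RC will assess the participant at 30 minutes post-procedure for his/her Horner’s syndrome", and each of ptosis, scleral injection and miosis is rated "0 for absent, 1 for slight, 2 for obvious". SAP section 3 schedules the intervention at weeks 0 and 2.

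Three other provisions matter:
- SAP 8.1 sets the primary analysis on the ITT population, regardless of compliance.
- SAP section 7 asks sites to keep following participants who stop treatment.
- SAP 8.6 says every secondary analysis will be run on both the ITT and the per-protocol populations.

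**The concern.** The cut-off of 12 selects active participants on two things at once: a full Horner's response and receipt of both injections. The first cannot be mirrored in the sham arm, because saline placed away from the ganglion is not expected to produce a block. The second can be mirrored, since sham participants are also scheduled for two procedures, but the SAP does not ask for it.

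Receipt of the week 2 procedure is a post-randomisation event. Participants who stop after one procedure may differ from those who continue in ways that also relate to the week 8 CAPS-5. If completion is required on one side only, the contrast mixes the effect of an effective block with a difference in completion.

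Readers are likely to take this analysis as the answer to what SGB does when the block works. The SAP does not say that the comparison is non-randomised.

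**Working it through.** **Inputs**
- Signs scored: 3 (Protocol 6.3; SAP 8.6.3).
- Score per sign: 0, 1 or 2 (Protocol 6.3).
- Ratings: one per procedure, at 30 minutes (Protocol 6.3).
- Procedures: 2, at weeks 0 and 2 (SAP section 3).
- Responder cut-off: total of 12 (SAP 8.6.3).

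**Step 1: reproduce the cut-off.**
Maximum per procedure = 3 signs × 2 points = 6.
Maximum over two procedures = 6 × 2 = 12.
The SAP's figure is reproduced as the maximum of the summed score, which fits its description of maximum density.

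**Step 2: find the ways to reach 12.**
Each procedure has 3 × 3 × 3 = 27 possible sign patterns, so two procedures have 27 × 27 = 729 pairs of patterns. Enumerating them, exactly one pair sums to 12: all three signs obvious both times (6 + 6). With one procedure the highest total is 6, which is below 12. The SAP does not say that 12 is a sum over both procedures, but no scoring in the documents reaches 12 from one.

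**Step 3: set the two selection rules side by side.**

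| | Active side | Sham side |
|---|---|---|
| Stated rule | Total score of 12 | Propensity score on baseline characteristics |
| Both procedures needed? | Yes, by arithmetic | Not stated |
| Can the rule reflect the week 2 procedure? | Yes | No, because it happens after baseline |

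**Step 4: can a one-procedure sham participant enter?**
Treatment may stop for reasons that include participant request, non-compliance and intercurrent illness (SAP section 6). Follow-up is to continue where possible (SAP section 7), so a week 8 CAPS-5 can exist after one procedure. The mirrored ITT analysis sets non-compliance aside (SAP 8.1). Nothing in SAP 8.6.3 or Protocol 8.2 removes such a participant.

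**Step 5: size.**
Let q be the share of sham comparators who missed week 2 but have a week 8 CAPS-5. Let g be the difference in mean CAPS-5 change between them and the sham participants who had both procedures. The sham mean then shifts by q × g. The documents give neither q nor the size or sign of g, so no value can be computed.

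**The case against.** The strongest reply is that a like-for-like version is already planned. SAP 8.6 also runs each secondary analysis per protocol, and the population in SAP 8.1 excludes withdrawals, losses to follow-up and any other deviation. A sham participant who missed a scheduled procedure should fall out there. This stands, with one reservation: a missed second procedure is not named among the exclusions, so the result is probable rather than stated. The point is therefore confined to the ITT version, which is still planned. The SAP does not say which version is to be read as the main one.

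Second, the SAP is silent rather than permissive. It does not expressly admit sham non-completers, and Protocol 8.2 speaks of an appropriate control sub-population. That is fair: the definition is incomplete, and the asymmetry follows from applying it as written.

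Third, a reader might infer that everyone who left the sham arm after one procedure stays in the comparison. The documents do not support this. Under SAP 8.3 the primary analysis uses available data without imputation, so a participant with no week 8 CAPS-5 contributes nothing. If the later imputation in Addendum 2 were carried over, such values would be imputed from baseline information and would not reflect an observed outcome after non-completion.

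Fourth, a reader might infer that the asymmetry must favour SGB. That assumes that sham participants who stop early improve less. They might instead stop because they improved, or for unrelated reasons such as illness or pregnancy. The documents report no outcomes for them.

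Finally, this is a supplementary analysis, the trial's conclusion rests on the ITT primary analysis, and SAP 9.1 already reports treatment completion by arm. This limits the consequence, but it is no reason to leave the selection rule incomplete.

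**Conclusion.** The point holds for the version of the Horner's responder analysis that mirrors the ITT primary analysis. A total of 12 requires 6 at each of two procedures, so active participants must have received both. Sham comparators are chosen on baseline variables alone, and those with one procedure and a week 8 CAPS-5 can enter. The comparison could be biased by the difference in completion.

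Neither direction nor size can be stated. Both depend on how many such sham participants there are and how their outcomes differ, and the documents give no figure for either. A claim of a particular number of CAPS-5 points, or of bias in favour of SGB, would go beyond the text.

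The conclusion rests on two readings: that 12 is the sum over both procedures, which is the only reading consistent with Protocol 6.3, and that the SAP's silence on sham completion means that no such condition applies. The per-protocol replicate probably avoids the problem. In either version, selection on Horner's response in the active arm remains, so the result is not a randomised comparison.

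**What to change.** Make three changes to SAP 8.6.3:

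1. State that the Post-Horner's total is the sum over the week 0 and week 2 procedures, and that 12 means 6 at each.
2. In the ITT version, restrict the sham pool to participants who received both procedures, and apply the propensity selection within that pool.
3. Label the result a non-randomised comparison. Matching on completion does not remove the selection on Horner's response in the active arm.

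No new data are needed. A case report form records each procedure (Protocol 3.1 and 9.1.6), and treatment completion is already to be summarised by arm (SAP 9.1). The cost is a few sentences and a sham pool smaller by the number who missed week 2, out of the 80 planned for that arm (Protocol 6.1). Since the existing addenda were written after unblinding, this change should be documented in the same way, with its timing stated.

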## **9. SUBJECT CHARACTERIZATION**

### **9.1 Subject Disposition**

Subject eligibility status will be summarized and listed by treatment group. The number of subjects screened; eligible; randomized; completing or discontinuing treatment; and completing follow up will be summarized by treatment group as well. Study withdrawals and reasons thereof will also be listed in a similar manner.

### **9.2 Protocol Deviations**

Protocol deviations are identified by site staff and via automated checks of the database. Protocol deviations will be listed by site with information such as type of deviation, time of occurrence, and reason. Incidence rate of protocol deviations will also be summarized overall and for each protocol deviation category by site.

## **10. ADVERSE EVENTS**

Reports of adverse events will be collected during the trial, and the Research Monitor is required to review all unanticipated problems involving risk to volunteers or others, Serious Adverse Events (SAE) and all volunteer deaths associated with the protocol and provide an unbiased written report of the event to the USAMRMC Office of Research Protections (ORP) Human Research Protection Office (HRPO).

An adverse event (AE) is any untoward medical occurrence in a clinical investigation participant administered a medicinal product and which does not necessarily have a causal relationship with this treatment. An AE can therefore be any unfavorable and unintended sign, symptom, or disease temporally associated with the use of a medicinal product, whether or not considered related to the medicinal product. AEs may also include pre- or post-treatment complications that occur as a result of protocol-mandated procedures (e.g. invasive procedures such as venipuncture, biopsy, etc.). Pre-existing events, which increase in severity or change in nature during or as a consequence of use of a medicinal product in human clinical trials, will also be considered AEs.

An AE does not include:

- Medical or surgical procedures (e.g. surgery, endoscopy, tooth extraction, transfusion); the condition that leads to the procedure is an adverse event.
- Pre-existing diseases or conditions or laboratory abnormalities present or detected prior to the screening visit, that do not worsen.
- Situations where an untoward medical occurrence has not occurred (e.g. hospitalization for elective surgery, social and/or convenience admissions).
- Overdose of either study drug or concomitant medication without any signs or symptoms unless the participant is hospitalized for observation.

### **10.1 Assessment of Adverse Events**

All AEs will be assessed by the investigator and recorded on the appropriate CRF page, including the date of onset and resolution, severity, relationship to study drug or study procedures, outcome and action taken with study medication.

The relationship to study drug therapy or study procedures should be assessed using the following definitions:

- **Definitely Not Related:** The participant did not receive the study drug and/or study procedure, the temporal sequence of the AE/SAE onset relative to administration of the study drug or performance of the procedure is not reasonable, or there is another obvious cause of the AE/SAE.
- **Possibly Related:** There is evidence of exposure to the study drug and/or study procedure, the temporal sequence of the AE/SAE onset relative to administration of the study drug or performance of the procedure is reasonable, but the AE/SAE could have been due to another cause.
- **Definitely Related:** There is evidence of exposure to the study drug and/or study procedure, the temporal sequence of the AE/SAE onset relative to administration of the study drug and/or study procedure is reasonable, the AE/SAE is more likely explained by the study drug and/or study procedure than by any other cause, and the AE/SAE shows a pattern

consistent with previous knowledge of the study drug or study drug class and/or the study procedure.

## **10.2 Serious Adverse Event (SAE)**

A **serious adverse event** (SAE) is defined as follows:

Any adverse drug experience occurring at any dose that results in any of the following outcomes:

- Death;
- Life-threatening situation (subject is at **immediate** risk of death);
- In-patient hospitalization or prolongation of existing hospitalization (excluding those for study therapy or placement of an indwelling catheter, unless associated with other serious events);
- Persistent or significant disability/incapacity;
- Congenital anomaly/birth defect in the offspring of a subject who received study drug;
- Other: medically significant events that may not result in death, be immediately life-threatening, or require hospitalization, may be considered a SAE when, based upon appropriate medical judgment, they may jeopardize the subject and may require medical or surgical intervention to prevent one of the outcomes listed in this definition.

### **Clarification of Serious Adverse Events**

- Death is an outcome of an adverse event, and not an adverse event in itself. In reports of death due to “Disease Progression”, where no other information is provided, the death will be assumed to have resulted from progression of the disease being treated with the study drug(s).
- All deaths, regardless of cause or relationship, must be reported for subjects on study and for deaths occurring within 30 days of last study drug dose or within 30 days of last study evaluation, whichever is longer.
- “Occurring at any dose” does not imply that the subject is receiving study drug at the time of the event. Dosing may have been given as treatment cycles or interrupted temporarily prior to the onset of the SAE, but may have contributed to the event.
- “Life-threatening” means that the subject was at immediate risk of death from the event as it occurred. This does not include an event that might have led to death, if it had occurred with greater severity.

- Complications that occur during hospitalizations are AEs. If a complication prolongs hospitalization, it is a SAE.
- “In-patient hospitalization” means the subject has been formally admitted to a hospital for medical reasons, for any length of time. This may or may not be overnight. It does not include presentation and care within an emergency department.
- The investigator should attempt to establish a diagnosis of the event based on signs, symptoms and/or other clinical information. In such cases, the diagnosis should be documented as the AE and/or SAE and not the individual signs/symptoms.

**Reason for addendum:**

After the approval of this clinical study plan and the analysis plan contained within it, clinical colleagues suggested that study results should include two additional efficacy outcome measures: the proportion of participants in each treatment arm who achieved a 10 point or greater improvement in the total symptom severity score (TSSS) on the CAPS-5 from baseline to week 8, and the proportion of participants in each treatment group who met CAPS-5 criteria for a PTSD diagnosis at baseline but no longer met criteria at 8-week follow-up. Additionally, clinical colleagues also suggested conducting a subgroup analysis on the primary outcome based on presence or absence of a clinical baseline PTSD diagnosis (based on the CAPS-5). The rationale for these investigative analyses was to provide additional information to increase interpretability and usability of results by clinicians. This addendum to the statistical analysis plan (SAP) details the investigative analyses that were performed, and hence this should be considered as post-hoc analyses that were determined post unblinding, and post approval of the original statistical analysis plan.

**Addendum:**

**Section 2.3.11. Decrease in Total Symptom Severity Score (TSSS) exceeded by 10 or more points.**

The proportion of participants in each treatment group who achieved a 10 point or greater improvement (reduction) in TSSS from baseline to week 8 was calculated. Contingency table analysis was used to compare both proportions descriptively.

**Section 2.3.12. Change in PTSD diagnosis status based on CAPS-5.**

The proportion of participants in each treatment group who met CAPS-5 criteria for a PTSD diagnosis at baseline but no longer met criteria at 8-week follow-up was calculated. Contingency table analysis was used to compare both proportions descriptively.

**Section 8.5.1. Subgroup Analysis on the Primary Outcome based on Baseline PTSD**

**Diagnosis.**

The model specified in the SAP (section 8.5) will be re-run but will also include baseline PTSD diagnosis and its interaction with treatment group. Full subgroup analyses will be reported if there is evidence of a subgroup by treatment interaction (a p-value of  $\leq 0.1$ ). However, if there is no evidence of a subgroup by treatment interaction, then a sensitivity analysis will be

conducted by re-running the primary analysis only among participants that had a baseline PTSD diagnosis.

ADDENDUM NUMBER 2 TO STATISTICAL ANALYSIS PLAN  
FOR PROTOCOL SGB-201

A Randomized, Sham-procedure-controlled, Blinded Study to Evaluate the Effectiveness and  
Acceptability of Right-sided Stellate Ganglion Block for Treatment of Posttraumatic Stress  
Disorder Symptoms

**SAP VERSION:** 10.0

**SAP DATE:** June 23, 2019

**Sponsor:** RTI International  
[name]  
Research Triangle Park, NC  
27709

**PREPARED BY:** RTI International  
[name]  
[name]  
Research Triangle Park, NC 27709-2194

**AUTHOR (S):** [name]  
[name]  
[name]

**Timing of Addendum:** \_\_\_ Before unblinding  X  After unblinding

**Reason for addendum:**

This addendum to the statistical analysis plan (SAP) is to document the methods to determine if the missingness observed in CAPS-5 week 8 data is random, and to describe the methods to impute the missing week 8 CAPS-5 values and the approach used to produce the final analysis.

The rationale for imputation of missing data for the primary outcome under the intention to treat (ITT) principle is that when the randomization process is disrupted by dropout or missing data outcomes, bias may be introduced that compromises the results.

The changes were made to provide additional clarification of the results in response to questions from journal reviewers.

